The purpose of this pilot study is to observe the effects of up to eight 8-weekly cycles of subcutaneous recombinant interleukin-2 (SC rIL-2) on levels of replication-competent HIV in blood CD4 T cells in 20 participants with chronically suppressed HIV infection (viral load <50 copies/mL) who are stable on the same ART regimen for at least one year and have a CD4 T cell count ≥ 350 cells/mm³. We hypothesize that IL-2 administration will result in a reduction of the replication-competent reservoir, as measured by the QVOA assay, compared to the baseline values in this population.

B.1. STUDY ENDPOINTS AND OUTCOME MEASURES

The primary endpoint of the study is the change in the level of replication-competent virus from baseline to the end of rIL-2 treatment, as measured by the Quantitative Viral Outgrowth Assay (QVOA).

B.2. PRIMARY OBJECTIVE

The primary objective will be to compare levels of replication competent HIV in circulating CD4 T cells before and after up to 8 cycles of rIL-2 administration. The frequency of CD4 T cells containing replication-competent virus in leukapheresis samples obtained at baseline and at the end of rIL-2 treatment will be enumerated using several state of the art methods. The primary readout for this objective will be measurement of replication-competent virus by Quantitative Viral Outgrowth Assay (QVOA) performed by [name]'s group at Accelevir.

B.3. SECONDARY OBJECTIVES

- 1) To examine the relationships between levels of replication competent HIV as identified by QVOA and other measures of HIV persistence:
 - a) the intact proviral DNA assay ([name]),
 - b) the Envelope Detection by Induced Transcription-based Sequencing (EDITS, [name]) performed on the same pre-trial and post-trial leukapheresis samples.
- 2) To explore the effects of rIL-2 administration on induction of HIV expression in vivo as measured by the EDITS assay and plasma HIV levels.
- 3) To examine the effects of rIL-2 administration on natural killer cell phenotype and function and on the ability of NK cells to limit HIV propagation in vitro.

C. METHODS

C.1. STUDY DESIGN

This is an open label pilot study of 20 participants with chronically suppressed HIV infection (viral load <50 copies/mL), stable on an ART regimen for at least one year, who have a CD4 T cell count ≥ 350 cells/mm³. All participants will receive rIL-2.

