3. HIV-1 infection, documented by and FDA-approved ELISA, EIA, or rapid antibody detection method, and confirmed by a second approved antibody-based test or by a positive approved HIV RNA detection assay.
4. CD4+ T cell count ≥ 350 cells/mm 3 .
5. HIV-1 RNA < 50 copies/mL obtained within 60 days prior to study entry performed with an FDA-approved HIV-1 RNA assay.
6. Adequate venous access and no other contraindications for leukapheresis.
7. Absolute neutrophil count (ANC) ≥ 1500 /mm 3 .
8. Hemoglobin level >10 g/dL.
9. Platelet count $\geq 100,000$ /mm 3 .

² Accelevir, data on file

10. Serum creatinine ≤ 1.5 mg/dL
11. AST and ALT < 2.5 times the upper limit of normal
12. TSH, T3, and T4 levels within the normal range of the processing laboratory.
13. Anti-thyrosine peroxidase (TPO) antibodies within the normal range of the processing laboratory.
14. Willing to comply with study-mandated evaluations; including not changing antiretroviral regimen (unless medically indicated) during the study period.
15. All participants must have received HAART, and had viral loads below the limit of quantification of the assay for at least 1 year. Participants who had intermittent isolated episodes of detectable low-level viremia < 500 copies RNA/mL flanked by viral loads below the limit of quantification of the assay will remain eligible.
16. On a stable combination antiretroviral regimen (no changes to treatment within 4 weeks of enrollment) including at least 3 medications and willing to continue on current antiretroviral therapy for the duration of the study, unless otherwise medically indicated.

C.4. EXCLUSION CRITERIA

1. Childbearing potential for female participants. For the purposes of this study, a woman is considered to be of childbearing potential if she is not postmenarchial, has not had a documented surgical sterilization procedure, has an intact uterus and at least 1 ovary, and has had a spontaneous menstrual period in the last 2 years.
2. Acute or chronic hepatitis C infection, defined as a positive plasma HCV RNA using any FDA-approved qualitative or quantitative test in a participant with a positive HCV antibody (HCV RNA testing is not required in participants with a negative HCV antibody). Participants who have completed a course of a direct-acting antiviral agent for hepatitis C and have a confirmed plasma HCV RNA level below the limit of detection of the assay 12 weeks or longer after completion of therapy will be eligible.

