3. Acute or chronic hepatitis B infection, defined as a positive HBV surface antigen or a positive HBV DNA.
4. History of advanced chronic liver disease, including cirrhosis, advanced liver fibrosis, severe portal hypertension, or manifestations or hepatic failure.
5. History of malignant disease that is not considered to be surgically or medically eradicated or that has required any form of therapy in the past 5 years.
6. Current diagnosis of congestive heart failure of any severity, uncontrolled angina or uncontrolled arrhythmias.
7. History of lung disease that has required pharmacologic treatment, oxygen supplementation, medical monitoring, or hospitalization in the previous year, or that is expected to cause persistent or recurrent pulmonary symptoms or impairment. Examples of the latter include but are not limited to chronic bronchitis, emphysema, and pulmonary fibrosis.
8. History or any features on physical examination indicative of a bleeding diathesis.
9. History or current diagnosis of thromboembolic disease, including deep vein thrombosis and pulmonary embolism, or family history of the same.
10. History of hypersensitivity to radiological contrast media or anticipated need for exposure to radiological contrast media during the study period.
11. Use of chronic corticosteroids, hydroxyurea, or immune-modulating agents (e.g., interleukin-2, interferon-alpha or gamma, granulocyte colony stimulating factors, etc.) within 30 days prior to enrollment.

NOTE: Use of inhaled or topical steroids is not exclusionary.

12. Breast-feeding.

13. Use of aspirin, warfarin or any other antithrombotic or antiplatelet agent during the 2-week period prior to leukapheresis.
14. History of autoimmune disorders, including but not limited to Crohn's disease, scleroderma, thyroiditis, inflammatory arthritis, myasthenia gravis, glomerulonephritis, systemic lupus erythematosus, and vasculitis.
15. Type 1 diabetes mellitus.
16. History of thyroid disease requiring that has required antithyroid or thyroid hormone replacement therapy at any time in the past.
17. Current continued use, or anticipated continued medical indication for nephrotoxic agents, including but not limited to aminoglycosides and other potentially nephrotoxic antimicrobials, indomethacin, high scheduled doses of other NSAIDs, and lithium salts.
NOTE: Low doses or limited duration of these agents (i.e., ≤ 14 days) is not exclusionary.

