- If a participant develops anti-Tpo antibody levels that are above the normal reference range of the laboratory, rIL-2 will be permanently discontinued.
- If a participant develops clinical signs or symptoms of hypo- or hyperthyroidism, rIL-2 will be permanently discontinued.

E.1.7. Renal Dysfunction

Participants who develop evidence of renal dysfunction will be referred for treatment by a qualified healthcare professional. Volunteers with serum creatinine $> 1.5 \text{ mg/dL}$ at screening will be excluded.

- Should serum creatinine increase to $> 2.0 \text{ mg/dL}$ but $\leq 3 \text{ mg/dL}$, rIL-2 will be interrupted. rIL-2 may be resumed at 3.5 million units twice daily when creatinine falls to $< 1.5 \text{ mg/dL}$. If creatinine remains $\leq 1.5 \text{ mg/dL}$ on the reduced dose of 3.5 million units twice daily, this dose will be continued to the end of study.
- If serum creatinine rises again to $> 1.5 \text{ mg/dL}$ while on the reduced dose of 3.5 million units twice daily, rIL-2 will be interrupted until it falls to $< 1.5 \text{ mg/dL}$ and then resumed at a dose of 2 million units twice daily. If serum creatinine then remains below 1.5 mg/dL , this dose

- will be continued to the end of study. If serum creatinine rises again to >1.5 mg/dL while on the reduced 2 million unit twice daily dose, rIL2 will be permanently discontinued.
- Should serum creatinine rise to >3 mg/dL, rIL-2 will be discontinued permanently

E.1.8. Malignant Conditions

All participants will be monitored for signs or symptoms of a malignant condition at each visit, and referred for treatment by a qualified healthcare provider if evidence of malignancy is found. Volunteers with a history of malignant disease that has not been fully resected and considered cured or in remission for at least 5 years will be excluded. Participants who develop a malignancy other than a basal cell skin carcinoma requiring no more than local excision during study will be required to discontinue study treatment permanently.

E.1.9. Viral Reactivation

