In ESPRIT, there was an excess of grade 4 clinical events in the rIL-2 recipients; the same excess was not seen in SILCAAT. Abrams and colleagues (42) have suggested this is via an impact on procoagulant pathways. In ESPRIT, patients with the highest CD4+ T-cell counts in the rIL-2 arm had the greatest relative risk of clinical events, including death. Perhaps, therefore, receipt of rIL-2 primes the patient for a proinflammatory state subsequently associated with more clinical events, and this is amplified in patients with the greatest CD4+ T-cell response to rIL-2, i.e. the ESPRIT cohort, which had higher baseline CD4+ T-cell counts than in SILCAAT. However, it is still important to remember that while rIL-2 receipt in ESPRIT was associated with more embolic

events, overall there was no excess of opportunistic diseases, death or cardiovascular disease and non-AIDS cancers compared with the ART-only arm.

I.6.1.1. Risk Mitigation Strategy for Serious Infections

Although there was no increased risk of infections in the two large phase III clinical trials of IL-2 administration (SILCAAT and ESPRIT), to mitigate the risk of serious infections, individuals with any of the following conditions will be excluded from enrolling in this study:

- A screening CD4 T-cell count <350 cells/mm³
- An absolute neutrophil count <1500 cells/mm³
- An active local or systemic infection
- Use of immunosuppressive or immune modulating therapy
- Use of any investigational agent
- Actively co-infected with HBV or HCV

If a serious infection develops, study drug will be held until the infection is adequately controlled. Study drug administration will be interrupted if the ANC is <1,000 cells/mm³.

I.6.1.2. Risk Mitigation Strategy for Hypersensitivity Reactions

To mitigate the risk of hypersensitivity reactions including anaphylaxis:

- Patients with a known allergy/sensitivity or any hypersensitivity to components of the study drug or its formulation will be excluded.
- The first dose of study agent will be administered in the Special Immunology Unit that has treated more than 50 patients with IL-2 on SILCAAT and ACTG 328 trials. Subjects will be monitored for a minimum of 30 minutes following the first dose of study drug by personnel with life support training and access to adequate life support equipment and resuscitation medication.
- A severe allergic reaction related to study treatment will be grounds for study treatment discontinuation.

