- Participants with serum creatinine $> 1.5 \text{ mg/dL}$ will be excluded from the study, and serum creatinine will be evaluated at each clinic visit.
- Should the serum creatinine increase to $> 2.0 \text{ mg/dL}$ but $\leq 3 \text{ mg/dL}$, rIL-2 will be interrupted. rIL-2 may be resumed at 3.5 million units twice daily when creatinine falls to $< 1.5 \text{ mg/dL}$. If the creatinine remains $\leq 1.5 \text{ mg/dL}$ on the reduced dose of 3.5 million units twice daily, this dose will be continued until the end of the study.
- If serum creatinine rises again to $> 1.5 \text{ mg/dL}$ while on the reduced dose of 3.5 million units twice daily, rIL-2 will be interrupted until creatinine falls to

< 1.5 mg/dL and then rIL2 may be resumed at 2 million units twice daily. If serum creatinine then remains below 1.5 mg/dL, this dose will be continued until the end of the study. If serum creatinine rises again to >1.5 mg/dL while on the reduced dose of 2 million units twice daily, rIL2 will be permanently discontinued.

- Should serum creatinine rise to > 3.0 mg/dL , rIL-2 will be discontinued permanently

I.6.1.5. Risk Mitigation Strategy for Malignancies

To minimize the risk of emergent or recurrent malignancies, subjects with a history of or active cancer will be excluded, and a review of interval diagnoses or medical events and a full or targeted physical exam will be performed at each visit. Additionally, concomitant immunosuppressive medications will be prohibited during the study.

I.6.1.6. Risk Mitigation Strategy for Viral Reactivation

The risk mitigation strategy for viral reactivation includes:

- Volunteers with evidence of active hepatitis B or C infection will not be enrolled in the study.
- Participants who develop herpes zoster will be required to discontinue treatment until completion of treatment and resolution of symptoms.
- Participants who develop a recurrence of herpes zoster or multidermatomal involvement will be required to discontinue study treatment permanently.
- Participants who develop a detectable HBV DNA while on study will require permanent study discontinuation.

I.6.1.7. Risk Mitigation Strategy for Blood Sample Collection and Intavenous Infusion

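### The risk section (I.6) states exclusions on cancer, infection, investigational agents, drug allergy and platelets that the eligibility criteria in C.3 and C.4 do not enforce

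*Combined protocol and SAP*

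**What the plan says.** **Cancer.** Three sections give three rules. I.6.1.5 states that "subjects with a history of or active cancer will be excluded". Criterion 5 in C.4, repeated in the synopsis, excludes malignant disease "not considered to be surgically or medically eradicated or that has required any form of therapy in the past 5 years". E.1.8 excludes volunteers with a "history of malignant disease that has not been fully resected and considered cured or in remission for at least 5 years".

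**Infection, investigational agents, drug allergy.** I.6.1.1 lists conditions that bar enrolment. Among them are an active infection, whether local or systemic, and "Use of any investigational agent". I.6.1.2 adds: "Patients with a known allergy/sensitivity or any hypersensitivity to components of the study drug or its formulation will be excluded". None of these is a specific item among the 21 exclusion criteria in C.4 or in the matching synopsis list.

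**Platelets.** I.6.1.4.2 and E.1.4 keep out anyone below 150,000/mm³. Criterion 9 in C.3 and in the synopsis accepts 100,000/mm³ and above.

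**ART stability.** Section B describes participants "who are stable on the same ART regimen for at least one year". Criterion 16 in C.3 asks for a stable regimen, defined as "no changes to treatment within 4 weeks of enrollment". C.6 combines one year of HAART with 4 weeks without change, and criterion 15 in C.3 requires one year of viral suppression.

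**The concern.** Section C.3 introduces its list as the conditions for enrolment, so sites can be expected to screen from C.3 and C.4. Section I.6 tells an ethics board or safety committee how known risks of rIL-2 are contained, and I.7.2 relies on that account as the study's protection against specific risks. Where I.6 is stricter than the list, or names an exclusion that the list lacks, the stated protection depends on someone remembering I.6 or using discretion.

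The stakes are mainly safety and consistent application. A person with a documented allergy to the study drug could pass every specific criterion. Two staff members could also decide differently on the same volunteer, depending on which section they had open.

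**Working it through.** No formula applies. The check compares each exclusion in I.6.1.1 to I.6.1.6, and the ART wording in B and C.1, with the numbered criteria in C.3 and C.4. The cases below are hypothetical and only show where the rules part.

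| Volunteer | C.3 / C.4 as listed | Other section |
|---|---|---|
| Cancer eradicated by drug treatment, no therapy for more than 5 years | Admitted by C.4 #5 | Excluded by I.6.1.5; under E.1.8 it depends on whether resection is required when there is remission |
| Cancer fully resected less than 5 years ago, considered cured | Excluded by C.4 #5 if surgery counts as therapy | Excluded by I.6.1.5; under E.1.8 it depends on whether the 5 years apply to cure or only to remission |
| Known allergy to a study-drug component | No specific criterion | Excluded by I.6.1.2 |
| Using an investigational agent that is not immune-modulating | No specific criterion | Excluded by I.6.1.1 |
| Active local infection that is not a serious illness | No specific criterion | Excluded by I.6.1.1 |
| Platelets from 100,000 to below 150,000/mm³ | Admitted by C.3 #9 | Excluded by I.6.1.4.2 and E.1.4 |
| Suppressed, regimen changed 5 to 51 weeks before enrolment | Admitted by C.3 #15 and #16 | Outside the section B description |

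**Nearest listed items.** C.4 #10 concerns hypersensitivity to contrast media only. C.4 #11 covers immune-modulating agents within 30 days, not investigational agents in general. C.4 #20 covers serious illness within 30 days and depends on the investigator's judgement. C.4 #21 is a general discretionary clause. Each reaches the missing exclusions only in part or by judgement.

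**On-study consequence.** C.6 prohibits any medication that meets the exclusion criteria. F.1 makes the need for a prohibited medication a ground for permanent discontinuation, citing the exclusion criteria and C.6. Because C.4 has no investigational-agent item, that chain does not prohibit such agents during the study either.

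**Platelet gap.** The two floors differ by 150,000 − 100,000 = 50,000/mm³. E.1.4 interrupts dosing when the count falls to 100,000/mm³ or below. The distance from entry floor to interruption is therefore 150,000 − 100,000 = 50,000/mm³ under I.6.1.4.2 and 100,000 − 100,000 = 0 under C.3 #9.

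**What agrees.** I.6 matches C.3 and C.4 on CD4 count (350 cells/mm³), ANC (1500 cells/mm³), AST and ALT (2.5 × ULN), creatinine (1.5 mg/dL), thyroid tests and anti-TPO, hepatitis B and C, and venous thrombosis. The immune-modulator exclusion agrees broadly, although C.4 #11 adds the 30-day window.

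**Count.** Five exclusions in I.6 do not match: cancer history, active infection, investigational agent, study-drug allergy and platelets. Section B's ART wording is one further, minor mismatch.

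**The case against.** The strongest reply is that the documents show which text governs. C.3 presents itself as the enrolment list, I.4 refers to the clinical protocol for the inclusion and exclusion criteria, and the synopsis agrees with C.3 and C.4 on every disputed item. On this view I.6 only describes risk controls. As a guide to what sites will do, that is fair. It does not remove the conflict. I.6 is itself protocol text, and it says that these people will be excluded. A summary may shorten a list, but it should not add exclusions or state a stricter rule. E.1.4 and E.1.8, outside section I, depart from the list as well.

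A second reply is that the gaps are covered elsewhere. D.3.2 requires allergies to study medications to be documented, C.4 #20 catches serious infection, and C.4 #21 allows any exclusion. These provisions make it less likely that an allergic or acutely ill person is dosed. Recording an allergy is still not excluding for it, and discretion is not the exclusion that I.6 states.

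On ART, the reply largely stands. Only section B says the same regimen. C.1 speaks more loosely of an ART regimen and can be read with C.6, and C.3 #15 does enforce a year of suppression. A reader might infer that a recent switch would distort the pre/post reservoir comparison in this single-arm trial. The documents do not support that. None of their text links a switch under suppression to a change in QVOA, A.1 describes the latent pool as long-lived with little decay, and C.2.1 plans adjustment for regimen type at entry and duration of suppression.

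It is also true that the trial is small, with up to 20 participants recruited mainly from one clinic.

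**Conclusion.** The inconsistency is real and should be corrected. Of the five mismatched exclusions in I.6, three have no specific criterion in C.4 or the synopsis, and two (cancer and platelets) are stated under conflicting rules. The ART wording in section B is a minor addition.

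Three stronger readings should be resisted. The risk section is not unreliable throughout, since most of its thresholds agree with C.3. C.4 #5 and E.1.8 do not share one 5-year cancer rule: C.4 requires eradication together with five years free of therapy, while E.1.8 turns on resection, cure and remission. Nothing here shows bias in the primary analysis or that anyone has been wrongly enrolled.

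The conclusion assumes only that sites screen from C.3 and C.4. If they also apply I.6, the practical gap narrows, but the contradictions on cancer and platelets remain.

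**What to change.** Reconcile I.6, E.1 and B with C.3, C.4 and the synopsis, so that each exclusion appears in the same words wherever it is stated or is removed:

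- For active infection, investigational agents and study-drug hypersensitivity, either add a numbered criterion to C.4 and the synopsis or delete the statement from I.6. If an investigational-agent criterion is added, give its time window and confirm that C.6 and F.1 pick it up.
- State one cancer rule in I.6.1.5, C.4 #5, E.1.8 and the synopsis, worded so that it is clear to which conditions the 5 years apply.
- State one platelet threshold in I.6.1.4.2, E.1.4, C.3 #9 and the synopsis, and check it against the interruption threshold in E.1.4.
- State one ART-stability rule in B, C.1, C.3 #16 and C.6.

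Which clinical rule governs is for the sponsor to decide; this point takes no position. The cost is an amendment to protocol wording and possibly a few more screen failures if the stricter versions are kept.
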